7.2 On-Study/Follow-up Visits

Each intervention visit consists of (1) participation in a parenting skills class followed by (2) participation in a peer support therapeutic group. The 8 sessions of parenting class include:

1. Getting Acquainted and Destination Adulthood
2. Effective Speaking Skills
3. Effective Listening Skills
4. Effective Problem Solving Skills
5. Connecting with Your Child: (a) Bonding Through Play and Reading, (b) Parenting Adolescents
6. Bonding through Emotion Coaching
7. Directions and Encouragements
8. Advocating for Your Children

Parenting skills classes last 2-2.5 hours. They are delivered by two trained facilitators. They are delivered remotely over Zoom. Participants are at home or other location of their choice. Attendance is tracked.

A 30-minute break is provided after the end of the parenting skills class. Then participants return to the remote Zoom session and participate in a therapeutic peer support group. These groups last one hour. They are facilitated by trained and licensed clinicians (e.g., social workers, counselors, psychologists).

All procedures and activities are provided solely for research purposes.

The final study visit for the intervention itself occurs after the final parenting skills class, usually one week later, where a graduation ceremony and celebration takes place. The final study interaction occurs three months after the post-test interview is completed when the 3-month follow-up interview takes place.

7.3 Early Termination/Withdrawal Visit

Subjects who terminate or are withdrawn early from the study will have one final visit to follow up regarding adverse events, collect study materials that are on loan (e.g., computer or tablet), and if applicable, to refer person or family to appropriate support services in the community.

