In addition to the classroom component that PIO provides, the program will offer a therapeutic component. These sessions will also be done virtually. Weekly, those receiving services from Pathways for Parents after Incarceration will be invited to take part in a remote peer support group-style group session led by a provider within the community, Anesis Family Therapy. This component of the program is rooted in systems therapy and uses narrative therapy, trauma focused cognitive therapy, and motivational interviewing techniques. This aspect promotes fathers' and caregivers' ability to identify their values and skills so they can effectively confront the challenges (both instrumental and relational) that they face during their reentry period and as family members working to support the fathers. These sessions will run for 45-60 minutes following the classroom portion (PIO).

The program (both classroom and therapeutic peer support) will be offered weekly in virtual, remote format on for 8 continuous weeks (the 9th week will be a class graduation/celebration). Any participant that does not have access to a computer will be loaned laptops or tablets and internet hotspots. The structure of the sessions are as follows:

5:00pm - virtual classroom opens and PIO course activities begin
7:00pm - PIO class concludes and 30 minute break begins
7:30pm - therapeutic peer support
8:30pm - wrap up

These sessions will provide gift card or cash incentives for attending and completing class material. Food will be delivered to their home in lieu of providing food in person during group meetings as was originally planned before COVID-19.

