3.0 STUDY OBJECTIVES AND ENDPOINTS

The aims of the pilot feasibility trial are to demonstrate:

- a) client acceptance of the treatment (e.g., retention)
- b) ability to recruit sufficient numbers of participants
- c) feasibility of delivery with the clients and therapists in the designated treatment settings

Specified measures will be collected at various times (e.g., client experience and satisfaction at post-intervention time points; outcome measures at pre- and post-intervention time points). Key outcome measures will assess father involvement, extended family relations, and child outcomes in addition to self-report criminal behavior, substance use, and recidivism for the fathers. Waves of data collection will occur: 1) prior to beginning the program, 2) immediately following the program, and 3) 3-months after completing the program. Data collection will be done with the father, caregiver, and child. This will be done virtually either by phone with research team members reading prompts to participants or by video conferencing where team members can virtually share screens and walk through documents together, or virtually with

research team members reading prompts and writing down answers. If not possible, it would take place in a private setting (ideally outdoors) where researchers and participants can be safely socially distanced.

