6.2 Study Intervention Compliance

Adherence to the protocol will be assessed by documenting the number of participants recruited, consented and enrolled, and attendance of participants in weekly PIO and therapeutic sessions. Completion of study interviews (measures and qualitative interviews) will also be tracked. To remain an active participant in the study, participants must attend all PIO sessions and if any are missed, attend a makeup session with a coach. Attendance records are carefully monitored and tracked. Participants who drop out of the study once the sessions begin will not be replaced.

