9.4 Statistical Methods

Primary outcomes will be assessed using descriptive statistics. Specifically, count data (e.g., number of enrolled participants who complete the intervention) are presented using percentages. Continuous measures presented as a score on a scale (e.g., provider adherence scores) are presented with means and standard deviations, and minimum and maximum scores.

Secondary outcomes will be assessed using paired sample t-tests to estimate changes between the scales at baseline and post-test. Two-tailed tests with .05 p-values will be used.

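### Leavers count in retention and attendance, but the plan does not provide for collecting their satisfaction or their reasons for leaving

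*Combined protocol and SAP*

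**What the plan says.** All references are to the combined protocol and SAP.

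- **Aim.** Section 3.0 lists as aim (a) "client acceptance of the treatment (e.g., retention", so retention is the named example of acceptance.
- **Self-report.** The same section gives as an example of measurement timing "client experience and satisfaction at post-intervention time points". Its three data-collection waves fall before the program, immediately after it, and three months after completing it.
- **Early leavers.** Section 7.3 gives those who terminate or are withdrawn one final visit. They "will have one final visit to follow up regarding adverse events, collect study materials that are on loan" and, where applicable, the visit serves "to refer person or family to appropriate support services in the community". Nothing else is listed.
- **Behavioral evidence.** Section 6.2 documents "attendance of participants in weekly PIO and therapeutic sessions" and does not replace people who drop out once sessions begin. Section 9.4 gives as an example of a primary count the "number of enrolled participants who complete the intervention".
- **Staying active.** Section 6.2 adds: "To remain an active participant in the study, participants must attend all PIO sessions", with a makeup for any that are missed.
- **Analysis set.** Section 9.3 restricts the analyses to people who completed the intervention and both interviews. Section 9.5 drops anyone without a post-test. Neither section exempts the feasibility outcomes.

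**The concern.** Acceptance has two kinds of evidence in this plan: what people do (attend, complete) and what they say (experience, satisfaction). Leavers supply the first but, as the plan stands, not the second.

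This has two consequences. The satisfaction result will describe people who found the program acceptable enough to finish. And the pilot will know how many left without knowing why. A father who rejected the content, one who could not manage the remote format or the schedule, and one who was re-incarcerated are all simply non-completers. Section 4.1 says the goal is to identify what a later randomized trial will need, and Section 2.1 makes refining operational methods a central purpose. Reasons for leaving serve both directly.

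The plan already accepts this logic at an earlier stage: Section 8.1 keeps screening data in order to learn who was ineligible and why. It has no counterpart for people who start and then stop.

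The gap is in data collection. Widening the Section 9.3 analysis set would not close it alone, because there would be no answers to analyze.

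**Working it through.** The plan states no figure for acceptability or dropout, so there is none to reproduce. The check has a textual part and an illustration.

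**Text, side by side**

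| Evidence on aim (a) | Completers | Leavers |
|---|---|---|
| Attendance (6.2, 7.2) | yes | yes, until they leave |
| Completion among enrolled (9.4) | yes | yes, as non-completers |
| Experience and satisfaction (3.0) | yes, post-intervention | not provided for |
| Reason for leaving | not applicable | not provided for (7.3) |

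Sections 9.3 and 9.5, read literally, conflict with Section 9.4. If only completers are analyzed, completion is 100% by construction. With the enrolled denominator of Section 9.4, every leaver lowers it. They would also exclude any satisfaction answers newly obtained from leavers.

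**Illustration**

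Inputs: N = 15 fathers (Section 1.1). Assumptions not in the documents: all 15 start, L = 5 leave, and S = 9 of the 10 completers are satisfied. Let k be the number of leavers who would say they were satisfied (0 to 5).

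- Reported satisfaction = S / (N − L) = 9/10 = 90%.
- Satisfaction among all starters = (S + k) / N = (9 + k)/15.

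| k | All starters | Reported minus all starters (points) |
|---|---|---|
| 0 | 9/15 = 60.0% | +30.0 |
| 1 | 10/15 = 66.7% | +23.3 |
| 2 | 11/15 = 73.3% | +16.7 |
| 3 | 12/15 = 80.0% | +10.0 |
| 4 | 13/15 = 86.7% | +3.3 |
| 5 | 14/15 = 93.3% | −3.3 |

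The report is too high whenever leavers are less satisfied than completers. Here that means k/5 below 9/10, which is every case except k = 5.

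Varying the assumed number of leavers, with one dissatisfied completer each time:

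| Leave | Completion | Reported satisfaction | Range among all starters |
|---|---|---|---|
| 2 | 13/15 = 86.7% | 12/13 = 92.3% | 80.0% to 93.3% |
| 3 | 12/15 = 80.0% | 11/12 = 91.7% | 73.3% to 93.3% |
| 4 | 11/15 = 73.3% | 10/11 = 90.9% | 66.7% to 93.3% |
| 5 | 10/15 = 66.7% | 9/10 = 90.0% | 60.0% to 93.3% |
| 6 | 9/15 = 60.0% | 8/9 = 88.9% | 53.3% to 93.3% |

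The width of the range is L/N. Reported satisfaction stays near 90% throughout, while the completion percentage registers every leaver. Adding the 15 caregivers does not change the pattern: with 10 of 30 leaving and 18 of 20 completers satisfied, the report is again 90% and the range is 18/30 = 60.0% to 28/30 = 93.3%.

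**The case against.** A reader might infer that leavers contribute nothing to aim (a). The documents do not support that. Retention is the plan's own example of acceptance, attendance is tracked, drop-outs are not replaced, and the Section 9.4 count is taken among enrolled participants. This objection stands in full: what is missing is leavers' ratings and reasons.

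A reader might also infer that the satisfaction result is certain to be too high, by 10 to 23 points. That interval comes from taking only 1 to 3 satisfied leavers out of 5. Someone who left because of schedule or re-incarceration may have liked the program, and with all five satisfied the report would be slightly too low. Upward bias is the likely direction, not a certainty.

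The wording of Section 3.0 is illustrative rather than exhaustive, and the instruments and qualitative interviews are not in the documents. An exit question on a form cannot be ruled out. Nor does any section expressly bar a post-test interview for someone who stopped attending. This limits the claim to what the plan provides for. But the full-attendance rule in Section 6.2, the single final visit in Section 7.3 and the exclusions in Sections 9.3 and 9.5 mean that such data are not planned.

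Payment is a weaker argument than it looks. Sessions carry "gift card or cash incentives for attending and completing class material", which may raise retention among those who stay. But someone who leaves despite payment is, if anything, clearer evidence of non-acceptance. Payment does not make retention uninformative.

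Finally, this is a small pilot without randomization, its primary outcomes are descriptive, and no planned calculation fails without exit data. That is true and limits the severity. It does not remove the value of a cheap addition bearing on the first aim.

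**Conclusion.** The point holds in a limited form. Leavers are counted in attendance and in completion among enrolled participants, but the plan does not provide for collecting their satisfaction or their reasons for leaving. Self-reported acceptability will therefore come from those who stayed, and a completion percentage cannot say whether people left because they rejected the program, missed a session without a makeup, or met an outside obstacle.

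The size is unknown, because the documents give neither a dropout nor a satisfaction rate. With 5 of 15 fathers assumed to leave, a reported 90% is compatible with anything from 60% to 93% among all starters. That range shows how little the planned data could exclude; it is not an estimate of bias. The change is worth making as an inexpensive improvement. Nothing here invalidates the pilot.

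**What to change.** - **Section 7.3.** Add to the existing final visit the experience and satisfaction measure used at post-test, and one reason-for-leaving item with fixed categories (for example content, remote format, schedule, family conflict, re-incarceration, other). If an exit form already asks this, say so here.
- **Section 9.4.** Report satisfaction for everyone who attended at least one session, with completers and leavers shown separately and response counts for each. Tabulate the reasons for leaving.
- **Sections 9.3 and 9.5.** State that the completer-only and complete-case rules do not apply to the feasibility and acceptability outcomes, and that retention is computed on all enrolled participants. Without this, the new answers would be collected and then excluded.

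The cost is a minor amendment and a few more minutes at a visit already planned, with no new visit or staff. The length of the satisfaction measure is not in the documents, so its fit for people who attended only part of the program should be checked. Some leavers will decline, which is why the response counts matter.

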1.2 Schematic of Study Design

2.0 INTRODUCTION

2.1 Purpose

The purpose of the overall study, Promoting Healthy Development among Children of Fathers with Antisocial Behavior, is to build and test a preventive family-focused intervention in a feasibility study that promotes healthy development for children of previously incarcerated fathers and their children. The study has three specific aims, two of which have already been completed. The first was to conduct secondary data analyses to explore a series of questions that explored topics including fathers' history of antisocial behavior and criminality, children's psycho-social and behavioral health outcomes, father engagement and parenting behavior, maternal parenting practices, quality of parental relationship, and extended family involvement. The second aim included conducting semi-structured interviews with fathers, mothers, and relatives to improve understanding of the barriers to father engagement and challenges that families face as fathers return to the community following incarceration.

To that end, this protocol situates itself within the third and final aim, that of specifying treatment procedures (e.g., develop manuals, select measures, specify therapist training and adherence procedures) and establishing feasibility of the intervention (e.g., recruitment, enrollment, fidelity, adherence, retention, and safety). Specifically, this protocol is in regard to the feasibility of the intervention. The purpose is to test the intervention for empirical promise through a pilot feasibility trial. The aims of the pilot are to demonstrate: a) client acceptance of the treatment (e.g., retention), b) ability to recruit sufficient numbers of participants, and c) feasibility of delivery with the clients and therapists in the designated treatment settings.

The family intervention is based in a family systems model that includes all members of the family. Multiple family groups are used because previous research has found they are efficient forms of service delivery, build social support among participants, and improve parent-child interactions. Feasibility of the pilot must include all participants anticipated in the program model to test strategies, logistics, and measures.

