9.3 Subject Population(s) for Analysis

Participants who completed the full intervention and the pre- and post-test interview (including both father and caregiver participants) will be included in the analyses.

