9.5 Handling of Missing Data

Complete-case analysis will be used and participants with missing data (i.e., missing post-test interview) will be excluded from the analysis.

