10.2 Known Potential Risks

There is a risk of a confidentiality breach.

Participants may be upset by aspects of the research or content of the intervention program.

Participants may reveal personal, sensitive, or identifiable information when responding to open-ended questions.

Participants may reveal illegal behaviors due to the nature of the questions.

Participants may become fatigued or frustrated due to the length of the study.

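### Safety is named as part of feasibility, but adverse events are asked about only at the early-withdrawal visit, and nearly everyone asked falls outside the analysis set

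*Combined protocol and SAP*

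**What the plan says.** Section 2.1 (Purpose) describes the third study aim as including "establishing feasibility of the intervention (e.g., recruitment, enrollment, fidelity, adherence, retention, and safety"), so safety is one of six listed examples. It does not reappear in aims a to c of section 3.0, and sections 3.0, 9.1 and 9.4 name no safety outcome.

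Section 7.3 contains the protocol's only mention of adverse events: people who leave or are withdrawn early have "one final visit to follow up regarding adverse events".

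The contacts with people who stay are described without any such enquiry. Section 6.2 tracks recruitment, consent, enrolment, attendance and interview completion. For the classes, section 7.2 says "Attendance is tracked". Section 7.4 describes the 3-month contact as the last data collection.

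On analysis, section 9.3 states: "Participants who completed the full intervention and the pre- and post-test interview (including both father and caregiver participants) will be included in the analyses". Section 9.5 adds that "participants with missing data (i.e., missing post-test interview) will be excluded from the analysis". Section 9.4, however, gives as its example of a primary count the "number of enrolled participants who complete the intervention", which needs everyone enrolled as its base.

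Section 10.2 lists a relevant harm in advance: "Participants may be upset by aspects of the research or content of the intervention program".

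**The concern.** Whether a person is asked about adverse events depends on whether that person leaves, and leaving is also what usually removes the person from the analysis set.

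The plan's own handling of distress strengthens the link. Section 10.3 lets participants skip or withdraw from anything that upsets them. Section 6.2 requires every parenting class to be attended or made up to stay active, and section 9.3 requires the whole programme to be completed. Someone who reacts to distress by stepping back therefore tends to drop out of the analysed data. Someone who was upset but carried on is not asked.

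At stake is what a report of few or no adverse events would mean. It could reflect who was asked as much as what happened. Section 4.1 says the pilot is meant to identify what a later randomised trial needs. A harms procedure not tried on people who stay would go into that trial untested.

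**Working it through.** The plan gives no safety rate, target or dropout rate, so there is no figure to reproduce. The main check is textual; the arithmetic only illustrates scale.

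**Step 1: who is asked, and who is analysed**

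| Participant | Planned adverse-event enquiry | In the 9.3/9.5 set |
|---|---|---|
| Leaves before finishing the programme or before the post-test | Yes (7.3) | No |
| Withdraws after the post-test, before the 3-month interview | Yes (7.3) | Yes, because 9.3 does not require the 3-month interview |
| Completes everything | None written (6.2, 7.2, 7.4) | Yes |

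The two groups overlap only in the second row.

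**Step 2: inputs for the illustration**

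- Adults: 15 fathers + 15 caregivers = 30 (synopsis). This is a planning figure: under section 5.3 a father may enrol without a caregiver.
- All participants: 47 (synopsis total).
- Dropout: not stated; 10%, 20%, 30% and 40% assumed.
- Every leaver is assumed to attend the 7.3 visit, so the numbers asked are upper values for each dropout rate.

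**Step 3: formulas**

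- Number asked: m = 30 × dropout.
- One-sided 95% upper bound with zero events among m asked: 1 − 0.05^(1/m).
- Chance of at least one event among m asked at an assumed true rate of 10%: 1 − 0.9^m.

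**Step 4: results for 30 adults**

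| Assumed dropout | Asked | Not asked | Upper bound, zero events | Chance of ≥1 event at a 10% rate |
|---|---|---|---|---|
| 10% | 3 | 27 | 63.2% | 27.1% |
| 20% | 6 | 24 | 39.3% | 46.9% |
| 30% | 9 | 21 | 28.3% | 61.3% |
| 40% | 12 | 18 | 22.1% | 71.8% |
| All 30 asked | 30 | 0 | 9.5% | 95.8% |

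For all 30 asked: 1 − 0.05^(1/30) = 0.095. The upper limit of a two-sided exact 95% interval for 0 of 30 is 1 − 0.025^(1/30) = 0.116.

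Counting children (47 participants, rounded), 5 to 19 would be asked at 10% to 40% dropout, with zero-event bounds of 45.1% to 14.6%. Asking all 47 gives 1 − 0.05^(1/47) = 6.2%.

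**Step 5: reading the bounds**

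The first four rows describe leavers only. They extend to everyone enrolled only if leavers and stayers have the same event rate, which is doubtful when distress is a possible reason for leaving. More dropout narrows the bound but does not remove that selection.

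**The case against.** The other side has several fair points.

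- **Weight of safety.** It appears once, in a list of examples, and the stated aims are acceptance, recruitment and delivery. This stands: a reader might infer that a safety endpoint was promised, and none was. The gap is that safety is named and then given no outcome, no enquiry for all enrolled and no reporting rule.
- **Exclusion is not total.** A reader might infer that everyone asked is removed and that no adverse event can reach the analysed data. Section 9.3 does not support that, since a person who withdraws after the post-test stays in. Section 9.4's enrolled-participant example also shows that 9.3 cannot govern every descriptive count, and nothing says that 9.3 governs adverse-event listings.
- **Something could be reported.** A reader might infer that safety cannot be assessed at all, or that no bound could be given. Staff could list events from the withdrawal visits and calculate a bound for leavers, as above. The wording of 7.3 about following up may also imply earlier recording, although no recording step is written.
- **Distress could surface elsewhere.** A reader might infer that distress among people who stay would go unnoticed. The plan has weekly groups led by licensed clinicians (7.2), client experience and satisfaction measures, child outcomes, fathers' self-reported substance use, criminal behaviour and recidivism (3.0), qualitative interviews (6.2) and mental health outcomes (9.1). These may reveal some harm. They are planned as treatment or outcomes, not as adverse-event collection, and the substance use, criminal behaviour and recidivism items cover fathers only.

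These points limit the claim. None supplies an adverse-event enquiry for completers or a summary over everyone enrolled.

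**Conclusion.** The point holds in this form: the protocol names safety as an element of feasibility but has no planned, unbiased way to assess it over everyone enrolled. Enquiry is written only for people who leave early, nearly all of whom fall outside the 9.3/9.5 set, and completers have no planned enquiry.

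This rests on the text and needs no assumed figure. The size does: with 30 adults, 10-40% dropout and every leaver seen, 18 to 27 adults would not be asked, and zero events would be compatible with a rate among leavers of up to 63%-22%, against 9.5% over all 30 if all were asked. The change is worth making because it alters what is collected and what can be concluded, and it is cheap.

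**What to change.** - **Sections 7.2 and 7.4:** add one standard adverse-event/distress item to the existing post-test and 3-month interviews for fathers, caregivers and children. Children would be asked only at these interviews, because the protocol does not describe them as attending the weekly sessions.
- **Section 6.2:** have session staff log any event that an adult attendee reports, next to the attendance record.
- **Sections 9.3 and 9.4:** state that adverse events are summarised descriptively for all enrolled participants, including those seen at the 7.3 visit, as counts and percentages with the number asked, separately from the completer set. The same edit should reconcile 9.3 with the enrolled base used in 9.4.

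If an interval is shown, say which kind: for 0 of 30 the one-sided 95% bound is 9.5% and the two-sided exact upper limit is 11.6%.

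The cost is one extra interview item, one log line and one table. It uses contacts already planned.
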